### 3. INVESTIGATIONAL PLAN

**Design.** This project is a feasibility pilot study to test the effects of vitamin C supplementation, and to obtain initial estimates of effect size to support a future RCT. The proposed vitamin C supplementation intervention study is a three-group, single blind, placebo controlled prospective design (control n=14, Vit C 500mg n=14, Vit C 1000mg n=14). The most commonly tested dose of vitamin C in current trials on vitamin C supplementation is 1 g/day. The primary endpoint to evaluate the effect of vitamin C supplementation is serum vitamin C level. The secondary outcomes include HF symptom burden, HRQOL, cardiac function, and oxidative stress. The variables would be measured in person at baseline and at 3 months include: HF symptom burden, HRQOL, PROMIS fatigue, depression and sleep disturbance, serum vitamin C level, biomarker of cardiac function (i.e., cardiac output using impedance cardiograph) and oxidative stress (8-iso-PGF2a isoprostane, see below in detail), as well as demographic, clinical, and other variables that can affect study outcomes (e.g., age, gender, race/ethnicity, body mass index, serum creatinine) and medications. HF symptom burden and HRQOL will also be measured at Month 1 and 2 by phone. We will also collect data to assess feasibility (recruitment, retention, attrition rates).

**Sample and Setting.** A total of 42 participants (14 per group) will be randomly assigned to either the control or the intervention group. Patients with HF will be recruited at the University of North Carolina Hospital internal medicine/cardiology outpatient clinics.

**Inclusion/Exclusion Criteria.** Inclusion criteria include patients (a) have a diagnosis of chronic HF. The diagnosis and etiology of chronic HF will be confirmed by a HF cardiologist using established criteria, (b) have undergone evaluation of HF and optimization of medical therapy, (c) are not taking any vitamin C supplementation at all or are willing to stop taking their current vitamin C supplementation, (d) able to read and speak English, (e) have >1 month from any inpatient hospitalization, (e) treating cardiology healthcare provider indicates the individual is a good candidate for this study that involves 3 months of vitamin C supplement of 500 mg/day, 1g/day, or placebo, (f) Per treating healthcare provider's assessment, patient's projected lifespan is greater than or equal to 6 months.

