## **8. SAFETY EVALUATIONS**

All participants will receive a phone call within 1 week after enrollment, and also at Month 1 and Month 2 to follow-up whether they are taking the investigational pills (vitamin C or placebo) daily and whether they have any adverse events from taking the investigational pills (see checklist in Appendix). If any adverse events were found/reported, we will follow them per recommendations of the medical monitor until the event resolves. [name], a nurse practitioner with specialty in heart failure management at UNC Meadowmont Cardiology clinic will serve as a medical monitor on this study. Any adverse event will be reported to [name] in 72 hours or less. [name] will determine the severity of the adverse events and advise whether the participant needs to stop taking the investigational pills, withdraw from the study, or any medical treatment is needed. We will follow [name]' advice immediately.

When subjects have AE (define as new signs and symptoms after taking investigational drugs, such as digestive distress--diarrhea, nausea, abdominal bloating and any other unanticipated adverse events that could possibly be related to the intervention). We will report to

[name] to determine the severity of the AEs (see below). When mild AE is determined, subjects will continue to take their investigational drugs without further treatment and the RA will keep following up subject's AE until AE resolves. When moderate AE is determined, we will ask subjects to stop taking their investigational drug, advise them to seek medical treatment, and continue to follow up until the AE resolves. If severity of any AE is more than moderate, we will ask subjects to seek for emergent medical treatment.

- Mild Adverse Event – Event results in mild or transient discomfort, not requiring intervention or treatment; does not limit or interfere with daily activities (e.g., insomnia, mild headache).
- Moderate Adverse Event – Event is sufficiently discomforting so as to limit or interfere with daily activities; may require interventional treatment (e.g., fever requiring antipyretic medication).
- Severe and undesirable Adverse Event – Event results in significant symptoms that prevents normal daily activities; may require hospitalization or invasive intervention (e.g., anemia resulting in blood transfusion).

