The adverse event information will be reviewed in our monthly team meeting to monitor subject safety. The PI will also monitor the rate of AEs occurring in this study and decide if it is reasonable in light of the rate of AEs in the current literature to continue the study with the medical monitor's input.

The research assistant is responsible to report any AE related to the study to [name] and the PI. The PI will work with the medical monitor to evaluate the event and make a determination of relatedness if the event is related to the study, as it occurs and for notifying the Associate Dean for Research of the UNC School of Nursing and UNC IRB of the occurrence of any adverse event. A scale on relatedness ranging from "Not related to" to "Definitely related to" (Not related to, probably not related to, possibly related to, definitely related to) will be used to evaluate relatedness. Any "definitely related" and "possibly related" events will be reported to the UNC IRB.

The PI will report to the UNC IRB any adverse events that are (1) unexpected, (2) related or possibly related to participation in the research, and (3) serious or suggest that there are new or increased risk(s) to subjects.

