## 9. DATA MANAGEMENT AND STATISTICAL ANALYSIS

Each participant will be assigned an anonymous ID. Data will be collected using touchscreen laptop computer, and the REDCap (Research Electronic Data Capture) system, a secure web-based application that is designed to support data capture for research studies.

All data analyses will be performed using SPSS 24.0. All estimates will be obtained along with 95% confidence intervals.

Descriptive statistics: All data with approximately symmetric distributions will be described by their mean and standard deviation, as well as number/frequency and percentage (for Aim 3) and variables with skew will be described by the median and interquartile range. Categorical variables will be shown as total number and proportion and will include: race, sex, NYHA functional class, and comorbidity. Associations between categorical variables will be tested by the Chi Square test ( $X^2$ ) or McNemar's test. Continuous variables will include symptom burden, PROMIS depression, fatigue, and sleep disturbance, HRQOL, cardiac function, serum vitamin C levels and biomarker for oxidative stress. Associations between categorical and continuous variables will be tested by t-test and analysis of variance (ANOVA). Associations between continuous variables will be tested using Pearson's correlation coefficient ( $r$ ) will be used to establish if the correlation coefficient is statistically different.

Efficacy analysis for the specific aims is described below:

The primary endpoint is serum vitamin C level. For Aim 1 to test the effect of a vitamin C supplementation intervention on the primary outcome (serum vitamin C level) from baseline to 3-month follow-up among 3 groups, we will use repeated measure of ANOVA to detect differences in the serum vitamin C level from baseline to 3-month follow-up in the intervention group and compared to the control group from baseline to 3-month follow-up.

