The secondary endpoints are symptom burden, HRQOL, cardiac function, and oxidative stress. For Aim 2 to test the effect of a vitamin C supplementation intervention on the secondary endpoint of HF symptom burden from baseline to 3-month follow-up among 3 groups, we will use repeated measure of ANOVA to detect differences in symptom burden from baseline to 3-month follow-up in the intervention group and compared to the control group from baseline to 3-month follow-up. Similarly, to test the effect of a vitamin C supplementation intervention on the secondary endpoint of HRQOL (cardiac function, and oxidative stress) compared to the control group, we will use repeated measure of ANOVA to detect differences in HRQOL (cardiac function, and oxidative stress) from baseline to 3-month follow-up in the intervention group and compared to the control group from baseline to 3-month follow-up.

Similar analysis will be done for adverse events. to test the effect of a vitamin C supplementation intervention on the frequencies of adverse events compared to the control group, we will use ANOVA to compare frequencies of adverse events during the 3-month period among 3 groups.

Sample Size and Power: The total sample size of 42 participants will be selected as a pilot feasibility study. With 42 patients (14 in each group) and an alpha level of .05, the power of the ANOVA F test to detect a significant group difference will be 80% if the effect size is 0.5.

Interim/safety Analysis. We plan to conduct the interim/safety analysis when we have 50% of the intervention sample, and the findings (as well as adverse events) will be reported to the medical monitor. The medical monitor will make decisions about the safety of continuing (or stopping) the protocol, providing recommendations for recruitment, retention, safety, and other issues as appropriate.

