**10. APPENDIX:**

**Checklist of adverse events for taking high dose of vitamin C supplement**

**Study #:** \_\_\_\_\_ **Data collector:** \_\_\_\_\_

**Date of follow-up:** \_\_\_\_\_ (for Week 1, Month1, Month2, Month3)

1. Diarrhea Yes No
2. Nausea Yes No
3. Abdominal bloating Yes No
4. Others: any other unanticipated adverse events/problems that occurred Yes No  
\_\_\_\_\_ (described what it is)

If any yes for item 1-4, describe in the box: 1) when did the event start, 2) how long did it last, 3) did the participant take any treatment/action, and 4) is it now resolved?

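### Adverse events: define what is counted and report participants affected per arm with exact 95% intervals, because the planned ANOVA gives no per-arm rate or upper limit (minor, cheap improvement)

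*Combined protocol and SAP*

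**What the plan says.** Section 9 (Data Management and Statistical Analysis) gives one analysis of adverse events: "we will use ANOVA to compare frequencies of adverse events during the 3-month period among 3 groups". It does not define a frequency and gives no other tabulation of adverse events.

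The data form is in the Section 10 appendix checklist, not in Section 9. Three named items and one open item are each answered Yes or No, for example "1. Diarrhea Yes No". The form is completed at four contacts ("for Week 1, Month1, Month2, Month3").

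Three general statements in Section 9 also bear on this:
- "All estimates will be obtained along with 95% confidence intervals". No method is named.
- "Categorical variables will be shown as total number and proportion and will include: race, sex, NYHA functional class, and comorbidity". Adverse events are not in the list.
- Associations between two categorical variables are assigned to the chi-square or McNemar test.

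Section 3 sets 14 participants per arm. Section 8 says "The PI will also monitor the rate of AEs occurring in this study" and has the PI weigh that rate against the literature, with the medical monitor's input. No document states an expected adverse event rate.

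**The concern.** An F test asks whether three means differ. A pilot's safety table should answer a simpler question: how many participants in each arm were affected, and how high could the true risk still be? With 14 per arm, that upper limit is the most useful number when few or no events are seen, and the planned analysis does not produce it.

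Two gaps leave the analyst to improvise. First, a participant with diarrhea at all four contacts could count once or four times. Four items at four contacts allow up to 4 × 4 = 16 yes-entries per person. Second, an analyst who takes the promised intervals from the ANOVA output would get intervals that fail when events are sparse. An arm with no events could then look more reassuring than 14 participants can justify.

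**Working it through.** **Inputs.** Three arms of 14, N = 42 (Section 3); alpha 0.05 (Section 9); Yes/No items at four contacts (Section 10). All event risks below are assumptions, because the documents give none. The figures take the unit as a participant affected or not (0/1), with all 14 per arm evaluable.

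**1. The plan's own figure.** Section 9 states 80% power for the ANOVA F test at effect size 0.5. Read as Cohen's f, the noncentrality is 42 × 0.5² = 10.5 on 2 and 39 df, which gives 80.3%. The figure reproduces, but it does not concern adverse events.

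**2. Is the F test sound on 0/1 data?** Full enumeration of the three binomial counts gives this true size for the nominal 5% test:

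| Common risk | 2% | 5% | 10% | 15% | 20% | 30% |
|---|---|---|---|---|---|---|
| Size | 0.4% | 2.2% | 3.4% | 3.5% | 4.0% | 5.2% |

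There is no material inflation. For 0/1 data with N = 42, F = 39X²/[2(42 − X²)], where X² is the Pearson chi-square. At the chi-square critical value of 5.99 this gives F = 3.24, which is also the F critical value on 2 and 39 df. The two tests named in Section 9 are therefore nearly the same test here, and the enumeration gives the same sizes for both.

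**3. Per-arm intervals.** Three ways of giving a 95% interval for x affected out of 14:
- Own SD: p ± t₁₃ √[p(1 − p)/13], with t₁₃ = 2.160.
- Pooled ANOVA variance: p ± t₃₉ √[(SSW/39)/14], with t₃₉ = 2.023 and SSW = Σ x(1 − x/14).
- Exact (Clopper-Pearson), from beta quantiles. For x = 0 the upper limit is 1 − 0.025^(1/n).

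*Counts 0/0/1, zero-event arms.* Own SD: 0 to 0. Pooled: SSW = 1 × (13/14) = 0.929, so the half-width is 2.023 × √(0.929/39/14) = 0.083 and the interval is -8.3% to 8.3%. Exact: 1 − 0.025^(1/14) = 0.232, so 0 to 23.2%.

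*Counts 0/1/3, highest arm (3/14 = 21.4%).* Own SD: -3.2% to 46.0%. Pooled: SSW = 0.929 + 3 × (11/14) = 3.286, half-width 0.157, interval 5.7% to 37.1%. Exact: 4.7% to 50.8%.

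*No event in any arm.* Both mean-based intervals have zero width and F is undefined. The exact upper limit for 0/42 is 1 − 0.025^(1/42) = 8.4%.

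**4. How often this would matter.** The chance of 0/14 in an arm is (1 − risk)^14.

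| Common risk | 2% | 5% | 10% | 20% |
|---|---|---|---|---|
| An arm has 0/14 | 75% | 49% | 23% | 4% |
| At least one arm has 0/14 | 98.5% | 87% | 54% | 13% |
| Own-SD coverage, one arm | 25% | 51% | 77% | 94% |
| Clopper-Pearson coverage | 99.8% | 99.6% | 99.1% | 98.8% |

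At 2% to 10% the own-SD shortfall is almost entirely the zero-event arms: given at least one event in the arm, coverage is 99.8% or more. The pooled interval is too narrow for the highest-risk arm when risks differ, with coverage of 80% (risks 5/5/20%), 81% (5/5/30%) and 86% (5/15/40%). At common risks of 20% to 30%, pooled coverage is 94% to 95% and own-SD coverage 89% to 94%.

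**The case against.** The strongest reply is that the plan proposes none of the poor intervals. Section 9 plans a comparison between groups, and its promise of 95% intervals is just as compatible with a binomial method. This stands: the documents show silence on method, not a defective method. The coverage figures describe what would follow from one natural but unstated choice.

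Several other points also stand.
- If a frequency means yes-entries, the ANOVA compares mean counts and the 0/1 figures do not apply.
- The number-and-proportion list may be illustrative, in which case per-arm counts are already implied and only the unit, denominator and interval method are missing.
- Sparse events are assumed. The row for any event includes an open item over four contacts and might not be sparse.
- Printed negative limits could simply be truncated. That would not repair the upper limits of 0% or 8.3%.

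A reader might go further and infer that ANOVA on these data is invalid or produces false positives. The sizes in step 2 do not support that. A split of 0/0/3 gives p = 0.038 by ANOVA and 0.095 by the Fisher-Freeman-Halton exact test, but a single split is not evidence of inflation.

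A reader might also infer that participant safety or the stopping decision depends on this analysis. The documents do not say so. Section 8 sends any event to the medical monitor "in 72 hours or less" and adds monthly review. Its monitoring of the rate does not cite the ANOVA or ask for an interval. The interim paragraph does not mention ANOVA either. The pilot's stated purpose, "to obtain initial estimates of effect size to support a future RCT", concerns effect sizes rather than event rates.

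**Conclusion.** The point holds as a minor, inexpensive improvement to reporting. The unit of an adverse event frequency is undefined, the promised intervals have no method, and the only named analysis gives neither a per-arm rate nor an upper limit. The gain is greatest when an arm has no events: 14 event-free participants are still compatible with a true risk of up to 23.2%. That number assumes participants affected as the unit and all 14 evaluable. The contrast with 0 to 0 or -8% to 8% further assumes that intervals would be taken from the ANOVA means. At common risks of 20% to 30% little would change. The planned F test can stand as a descriptive comparison.

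**What to change.** In the adverse event paragraph of Section 9:

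1. Make the main summary the number and percent of participants per arm with at least one event over the 3 months, overall and for each checklist item, counting each participant once per row.
2. State the denominator: participants who started study pills and had at least one adverse event contact.
3. Give Clopper-Pearson 95% intervals, including the upper limit when the count is zero (23.2% for 0/14 and 8.4% for 0/42 if all are evaluable; if only 12 in an arm were evaluable, 26.5% for 0/12).
4. List yes-entries per arm and contact alongside, so that recurrence is not lost.
5. Treat any three-arm test as descriptive. If one is kept, say what it is applied to, and reconcile ANOVA in this paragraph with chi-square for categorical associations earlier in the section.

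Newcombe score intervals for risk differences versus placebo, and an exact test in place of the F test, are optional. The first may need a macro or a second package, since Section 9 names only SPSS 24.0. The second loses some power: for assumed risks of 5/15/30%, 23% against 27% for ANOVA.

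The cost is SAP wording; the checklist already collects the data. The downside is that exact intervals are wide and conservative, with coverage of 97% or more at every risk checked.

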**10. APPENDIX:**

**Checklist of adverse events for taking high dose of vitamin C supplement**

**Study #:** \_\_\_\_\_ **Data collector:** \_\_\_\_\_

**Date of follow-up:** \_\_\_\_\_ (for Week 1, Month1, Month2, Month3)

1. Diarrhea Yes No
2. Nausea Yes No
3. Abdominal bloating Yes No
4. Others: any other unanticipated adverse events/problems that occurred Yes No  
\_\_\_\_\_ (described what it is)

If any yes for item 1-4, describe in the box: 1) when did the event start, 2) how long did it last, 3) did the participant take any treatment/action, and 4) is it now resolved?

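### The adverse event checklist is never completed before the first tablet and has no line for daily-activity limitation or grade: a minor gap in data capture that is cheap to close

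*Combined protocol and SAP*

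**What the plan says.** Section 8 (Safety Evaluations) has every participant phoned within a week of enrollment and again at Months 1 and 2, and asked "whether they have any adverse events from taking the investigational pills (see checklist in Appendix"). It defines an adverse event this way: "define as new signs and symptoms after taking investigational drugs, such as digestive distress--diarrhea, nausea, abdominal bloating". Other unanticipated events possibly related to the intervention also count.

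The same section sets the grades. Mild is "not requiring intervention or treatment; does not limit or interfere with daily activities". Moderate is "Event is sufficiently discomforting so as to limit or interfere with daily activities; may require interventional treatment". Severe is reached when normal activities are prevented. Tablets continue after a mild event and are stopped after a moderate one. The medical monitor is told of every event within 72 hours and assigns the grade.

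The checklist in Section 10 (Appendix) has Yes/No items for diarrhea, nausea, abdominal bloating and anything else. Its date line reads "for Week 1, Month1, Month2, Month3". For any Yes, a box asks "1) when did the event start, 2) how long did it last, 3) did the participant take any treatment/action, and 4) is it now resolved".

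For baseline, Section 5 lists demographic and clinical data, medications, questionnaires, impedance and blood. Section 8 (Patient Safety and Confidentiality) adds vitamin use, serum creatinine and kidney stone history. Section 7 describes the MSAS-HF as an 8-item instrument without naming the items.

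Section 9 compares the frequency of adverse events over the 3 months among the three groups by ANOVA. It does not use grade.

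**The concern.** Two facts that Section 8 relies on are not well served by the form that Section 8 points to.

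The first is whether a symptom is new. No one records diarrhea, nausea or bloating before the first tablet, so the answer comes from a participant already on tablets who is asked when the symptom began. A symptom that was present earlier and became worse has no recorded starting level, and the word new does not clearly admit it. Earlier symptoms may therefore be counted as events, or true worsening may be set aside. Both would blur the comparison of event frequencies among arms of 14.

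The second is whether daily activities were limited. This is the main fact separating mild from moderate, yet the form neither prompts for it nor records the resulting grade.

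**Working it through.** The plan gives no figure on this point, so there is none to reproduce. The check compares the form with Section 8 and then works out the direction of the effect on the Section 9 comparison.

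**1. Newness.** Section 8 requires: "define as new signs and symptoms after taking investigational drugs". The form is completed at Week 1 and Months 1, 2 and 3, with no completion before the first tablet. Of the baseline assessments listed in Sections 5 and 8, none is said to cover the three named symptoms, and the MSAS-HF cannot be assumed to cover them because its items are not given. The onset question does collect something: a recalled start can be set against the first-tablet date. It cannot show a change in level of a symptom that was already there.

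**2. Grade.** The element that runs through all three definitions is the effect on daily activities: none, some, or normal activities prevented. Need for treatment is a second element, partly captured by the question on treatment or action. For an untreated bout of diarrhea or bloating, the completed form is compatible with either mild or moderate. The form has no field for the grade once assigned, and the documents do not say where it is recorded.

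**3. Effect on the frequency comparison.** Let b be the share of participants with an earlier symptom, q the chance that such a participant is counted as having an event whether or not the symptom worsened, and p the true rate of new or worse symptoms in an arm. If b and q are the same in all arms:

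- observed rate = b × q + (1 − b) × p
- observed difference between two arms = (1 − b) × (p1 − p0)

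The term b × q cancels. With p1 = p0, the expected difference is zero for every b and q, so the gap does not create a difference. With a real difference, it shrinks by the factor (1 − b), whether earlier symptoms are all counted (q = 1) or all set aside (q = 0).

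To show the direction only, assume event rates of 10% on placebo and 40% on an active dose. None of these inputs is in the documents.

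- b = 0: 40 − 10 = 30 points
- b = 0.1: 0.9 × 30 = 27 points (q = 1: 19% v 46%; q = 0: 9% v 36%)
- b = 0.2: 0.8 × 30 = 24 points (q = 1: 28% v 52%; q = 0: 8% v 32%)
- b = 0.3: 0.7 × 30 = 21 points (q = 1: 37% v 58%; q = 0: 7% v 28%)

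These shrinkages are upper limits for each b. They give no credit to correctly recalled onset, to the monitor's inquiries, or to a participant with one earlier symptom who develops a different one.

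**4. Grade and the comparison.** Section 9 counts events and not grades, so the missing activity line does not enter the calculation in step 3.

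**The case against.** The strongest reply is that the checklist is a screening aid for phone calls and not the grading instrument. The medical monitor assigns the grade and may ask about daily activities; nothing in the documents prevents it. The research assistant follows each event until it resolves, and the team reviews events monthly. On newness, the form's first question is about onset, the first call comes within a week so recall is short at that contact, and the investigator and monitor also judge relatedness. Adverse events are neither a primary nor a secondary endpoint of this 42-person pilot.

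Most of this stands. It defeats a stronger reading that a reader might infer: that grading, stopping of tablets and the by-arm comparison all depend on information never collected. The documents do not support that. Onset and treatment are asked, the monitor can obtain more, and the by-arm comparison does not use grade. Nor do they support a claim that the comparison would be systematically distorted in favor of one arm, since randomization gives all arms the same expected background.

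What the reply leaves open is narrower. The documents do not say that the monitor interviews the participant, what the research assistant passes on, or where the grade is kept. The fact that mainly separates continuing from stopping is left to an unwritten question. Neither the onset question nor the relatedness judgment supplies a starting level against which worsening could be shown.

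**Conclusion.** The point holds as a minor one. The checklist has no completion before the first tablet, so newness rests on recalled onset and worsening of an earlier symptom cannot be shown or counted. This would dilute a real difference in event frequencies. Separately, activity limitation and the assigned grade are neither prompted nor recorded on the form, which leaves the basis of the grade undocumented but does not touch the frequency comparison.

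The documents do not fix a size, because they give no prevalence of the three symptoms. A reader might try to supply one by assuming a prevalence and computing how often two arms of 14 would differ by chance. That is ordinary binomial variation, which genuine new events at the same rate would also show, so it does not measure this gap. A reader might also infer that these data will choose the dose for the later trial. Section 3 says only that the pilot will give initial effect-size estimates to support one.

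The conclusion assumes that the Appendix form is the only adverse event instrument, as the documents present it, and that the baseline questionnaires do not already ask about these symptoms. If they do, the newness part largely falls away.

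**What to change.** Change data capture only:

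- Complete the same checklist once at the baseline visit, before the first tablet, and add that time point to its date line.
- In Section 9, state that the by-arm comparison counts events that are new or worse than the participant's own baseline.
- For each Yes item, add one line for effect on daily activities with three options matching Section 8 (not limited, limited, prevented), and a field for the monitor's grade.

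Leave the grade definitions and tablet actions in Section 8 unchanged.

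The cost is a one-page form revision and about two minutes at a visit that already administers questionnaires. Asking about the symptoms at baseline may slightly prime later reports, but equally in all arms.
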